4.3. Determination of Sample Size

Approximately 210 patients will be randomly assigned to receive orismilast 20 mg, 30 mg, or 40 mg BID or placebo for 16 weeks.

This sample size is based on assumptions that there is a difference of 25.0% in the percent change from baseline in EASI scores between each orismilast dose group with placebo, respectively, and that the common standard deviation in the percent change from baseline in EASI score is 43%. Using a 2-sided 2-sample t-test, 47 patients in each treatment group (188 in total) will achieve a power of 80% at the significance level of 5%. To account for an early dropout rate of approximately 10%, an additional 22 patients will be randomized.

4.4. Treatment Assignment and Blinding

Randomization will occur before the first study treatment administration, at the Baseline visit. Patients will be assigned randomly in a 1:1:1:1 ratio to 1 of 3 orismilast dose groups (20 mg, 30 mg, or 40 mg) or placebo. The randomization is stratified by site. All patients will be assigned to randomized study treatment using an Interactive Web Response System (IWRS).

A randomization list will be used to assign the treatments to each patient. The randomization list will be kept secured with access restricted to only the designated personnel directly responsible for labeling and handling the study drug until the study blind is broken at the end of study (database lock).

To facilitate the double blinding, the tablets will be packaged in the same type of blister, and the active and placebo tablets will have the same appearance (in terms of size, form, weight, and color). One dose consists of 2 identical tablets (a 10 mg or 30 mg orismilast tablet or a matching placebo tablet).

Blinding codes should only be broken in emergency situations for reasons of patient safety. The patient for whom the blind has been broken will be discontinued from the study and undergo the early termination procedures. The primary reason for discontinuation (the event or condition which led to the unblinding) will be recorded.

The Sponsor's safety staff may unblind the study drug assignment for any patient with an SAE. If the SAE requires that an expedited regulatory report be sent to 1 or more regulatory agencies, a copy of the report identifying the patient's study drug assignment may be sent to investigators in accordance with local regulations and/or Sponsor policy.

4.5. Administration of Study Medication

The patients will receive the study drug at the site directly from the Investigator or designee. The date of the first dose should be recorded in the source documents and recorded in the eCRF. At all site visits beginning with the Week 2 visit, patients will return all study drug, including packaging, dispensed at the previous visit, and it will be documented using the IWRS.

The patients will self-administer the study drug at home, and compliance with the protocol will be assessed at each visit beginning with the Week 2 visit. Compliance will be assessed by direct questioning and counting returned tablets during the site visits and documented in the source documents and relevant form. Deviation from the prescribed dosage regimen should be recorded.

A record of the quantity of study drug dispensed to and administered by each patient must be maintained and reconciled with study drug and compliance records. Study drug administration dates, including dates for administration delays and/or dose reductions, will also be recorded. Discontinuation for noncompliance is at the investigator's discretion and is to be noted on the eCRF.

4.6. Study Procedures and Flowchart

The Schedule of assessments is in Protocol Section 9.

5. Endpoints

5.1. Primary Efficacy Endpoint

• Percentage change in EASI score from Baseline at Week 16.

5.2. Secondary Efficacy Endpoints

Key Secondary Efficacy Endpoints:

- Patients achieving 75% reduction in EASI (EASI75) response at Week 16.
- Patients achieving a score of clear (0) or almost clear (1) and at least a 2-point improvement in IGA-AD at Week 16.

Other Secondary Efficacy Endpoints:

- Patients achieving a score of clear (0) or almost clear (1) and at least a 2-point improvement in IGA-AD at Weeks 2, 4, 8, 12, and 20.
- Patients achieving EASI75 at Weeks 2, 4, 8, 12, and 20.
- Patients achieving 50% reduction in EASI (EASI50) and 90% reduction in EASI (EASI90) response at Weeks 2, 4, 8, 12, 16, and 20.
- Percent change from Baseline in EASI at Weeks 2, 4, 8, 12, and 20.
- Change from Baseline in the peak pruritus NRS score at Weeks 1, 2, 4, 8, 12, 16, and 20.
- Patients achieving at least a 4-point improvement in the peak pruritus NRS from baseline at Weeks 1, 2, 4, 8, 12, 16, and 20 among patients with a baseline score ≥4.
- Change from Baseline in affected BSA at Weeks 2, 4, 8, 12, 16, and 20.
- Change from Baseline in DLQI score at Weeks 8, 16, and 20.
- Change from Baseline in POEM score at Weeks 2, 4, 8, 12, 16, and 20.
- Change from Baseline in PGIS score at Weeks 2, 4, 8, 12, 16, and 20.
- PGIC score at Weeks 2, 4, 8, 12, 16, and 20.
- Change from Baseline in sleep disturbance NRS score at Weeks 1, 2, 4, 8, 12, 16, and 20.
- Change from Baseline in skin pain NRS score at Weeks 1, 2, 4, 8, 12, 16, and 20.

5.3. Exploratory Endpoints

- Patients achieving at least a 2-point improvement in the peak pruritus NRS from baseline at Weeks 1, 2, 4, 8, 12, 16, and 20 among patients with a baseline score ≥4.
- Change from Baseline in pulmonary status NRS in patients with asthma at Weeks 4, 8, 12, 16, and 20.
- Patients achieving 100% reduction in EASI (EASI100) response at Weeks 2, 4, 8, 12, 16, and 20.

5.4. Pharmacokinetic Endpoint

• Plasma levels of the drug and its metabolites at Weeks 4, 8, and 16.

5.5. Safety Endpoints

• The occurrence, severity, and seriousness of treatment-emergent AEs (TEAEs) reported over the 16week Treatment Period and the 4-week Follow-up Period.

- Changes from Baseline in physical examination findings; vital signs measurements (body temperature, respiration rate, heart rate, and systolic and diastolic blood pressure measurements); and body weight over the 16-week Treatment Period and the 4-Week Follow-up Period.
- Clinically significant abnormal changes in ECG findings over the 16-week Treatment Period.
- Changes from Baseline in safety laboratory values (hematology, serum chemistry, and urinalysis) over the 16-week Treatment Period.
- Change from Baseline in HADS score at each visit except Week 1.
- C-SSRS score at each visit except Week 1.

5.6. Pharmacodynamic Endpoint

• Change from Baseline in skin biomarkers at Week 16 collected via tape stripping and analyzed using proteomic methods.

6. Analysis Populations

6.1. Randomized Population

The randomized population will include all patients randomized. Unless specified otherwise, this population will be used for patient listings and for summaries of patient disposition.

6.2. Safety Population

The safety population will include all randomized patients who receive at least 1 dose of study drug. The treatment group assignment in this population will be defined by the treatment actually received. This population will be used for the analysis of safety.

6.3. Intent-to-Treat Population

The intent-to-treat (ITT) population will include all randomized patients who receive at least 1 dose of study drug. The treatment group assignment will be designated according to initial randomization. The ITT population will serve as the basis for the analysis of efficacy.

6.4. Per-Protocol Population

The per-protocol (PP) population includes all randomized patients who receive at least 1 dose of study drug, have at least 1 post-Baseline EASI assessment, and who do not have any major protocol deviations affecting efficacy analysis. The treatment group assignment in this population will be designated according to initial randomization. Efficacy analysis for primary and key secondary endpoints will be repeated on the PP Population.

6.5. Protocol Deviations

Protocol deviation management at Syneos Health is detailed in Protocol Deviation and Non-compliance Management (3101.W02). For details on the process for defining analysis datasets refer to (Blind) Data Review and Definition of Analysis Sets SOP (3911). The Protocol deviation criteria are graded as minor and major.

Patients with a major protocol deviation affecting efficacy analysis will be excluded from the PP population. The list of major protocol deviations potentially leading to PP population exclusion includes at least the following deviations:

- Violations of inclusion or exclusion criteria.
- Use of disallowed medication (that may influence the interpretation of efficacy results).
- Non-compliance with study medication intake: less than 80% of total number of tablets during entire treatment period or during the last 4 weeks.
- Major deviation from study specific instructions/procedures.

The final list of patients who are to be included in the PP population will be determined at the Blinded Data Review Meeting (BDRM). The BDRM will occur when all or nearly all queries have been resolved and the database is near to final. For the BDRM meeting, a BDRM Preparation Plan will be prepared. This plan will detail further the types of protocol deviation criteria and will include, as a minimum: 1) the exact criteria which will be used to determine if a patient will be excluded from the PP population; 2) the listings which will be prepared for sponsor review in order to determine which patients to exclude from the PP population. Details of patient specific exclusions from the PP population will be detailed in the BDRM Report.

7. General Aspects for Statistical Analysis

7.1. General Methods

- All statistical analyses will be conducted using SAS[®] for Windows[®] Version 9.4 or higher.
- All data will be listed, and summary tables will be provided.
- In general, unscheduled visit data will be listed, but not included in the summary tables by visit. Unscheduled data will be included to identify the worst-case post-baseline for safety shift tables. Unscheduled data will be used in the statistical analysis to avoid missing data.
- Summary statistics will be presented by treatment group. For continuous variables, data will be summarized with the number of patients (N), mean, standard deviation, median, Q1, Q3, minimum, and maximum by treatment group. For categorical variables, data will be tabulated with the number and proportion of patients for each category by treatment group.
- There will be no adjustment for multiplicity, thus all p-values reported will be nominal.
- The randomized population will be used for patient data listings.
- Unless otherwise specified, listings will be sorted by randomized treatment, subject number and chronologically by assessment date and time.
- Missing records will be omitted from the listings, and missing data within a record will be left blank.
- Unless otherwise specified, baseline summaries will be presented for each treatment (Placebo, Orismilast 20 mg BID, Orismilast 30 mg BID, Orismilast 40 mg BID) and for Overall. Safety summaries will be presented for each treatment (Placebo, Orismilast 20 mg BID, Orismilast 30 mg BID, Orismilast 40 mg BID) and for Orismilast Total. Efficacy summaries will be presented for each treatment (Placebo, Orismilast 20 mg BID, Orismilast 30 mg BID, Orismilast 40 mg BID).

7.2. Key Definitions

Treatment period

The Treatment Period for this study is 16 weeks, from Day 1 to Week 16 (112 ± 3 days).

Study day

If the event date \geq date of first dose of IP, study day = event date – date of first dose of IP + 1. If the event date < date of first dose of IP, study day = event date – date of first dose of IP.

Baseline Value

Baseline value will be defined as the last non-missing value recorded prior to the first intake of study treatment.

Change from Baseline (CFB)

CFB = Post-baseline value – Value at baseline

Percentage change from baseline (PCFB)

PCFB = ((Post-baseline value – Value at baseline) / Value at baseline)*100%.

7.3. Missing Data

Missing data will be treated as missing, except in the following cases.

Efficacy

To ensure that we evaluate the effect of study treatment (and not the effect of study treatment + disallowed medications (e.g. topical medications)), patients efficacy data collected after date of first disallowed medication (which may influence efficacy assessments e.g. any medication given to control unacceptable atopic dermatitis symptoms) will be 'set to missing' / 'treated as missing' in the primary statistical analysis . If disallowed medication is introduced the same day as an efficacy assessment, the efficacy assessment will be used as is.

Missing data and data 'treated as missing' for the primary analysis of primary and secondary binary endpoints will be handled with the multiple imputation method, assuming Missing At Random (MAR) within arm.

For categorical efficacy endpoint based on a continuous variable, the multiple imputation will be first done for the continuous variable, then determine the category using the imputed values.

Secondary continuous endpoints will be analyzed based on observed data using an MMRM, thus using a modelling approach assuming MAR for missing data.

For a supportive analysis of key secondary efficacy endpoints missing data will be handled as non-response.

Safety

• Missing AE relationship will be imputed by 'definitely'.

- Missing AE severity will be imputed by 'Grade 3'.
- Missing or incomplete dates in safety data:

In all listings, missing or incomplete dates will be left as they have been recorded. However, for calculation / sorting / assignation based on dates, the following methods will be used:

- I. The most conservative approach will be systematically considered (i.e. if the onset date of an AE/concomitant medication is missing or incomplete, it is assumed to have occurred during the treatment period (i.e. a TEAE for AEs) except if the partial onset date indicates differently).
- II. A missing/incomplete date of medical history or disease diagnosis will be assumed to have occurred before any study treatment.

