#### 7 SELECTION OF STUDY POPULATION

#### 7.1 Inclusion Criteria

Patients are eligible to be included in the study only if all the following criteria apply at both the screening and baseline visits:

- 1. Capable of giving signed informed consent, which includes compliance with the requirements and restrictions listed in the Informed Consent Form (ICF) and in the protocol
- 2. Male and female patients aged at least 18 years at the time of signing the ICF
- 3. Body weight of greater than 40 kg at the time of signing the ICF
- 4. Diagnosis of AD for a minimum of 1 year (before the Screening visit) using the Hanifin and Rajka criteria
- 5. Moderate to severe AD (affected BSA of at least 10%, IGA-AD grade of at least 3, and EASI score of at least 16) at the screening and baseline visits
- 6. Candidate for systemic treatment or phototherapy for AD
- 7. Patients having a documented history of inadequate response to treatment with topical medications given for at least 4 weeks (at least 2 weeks for high potency topical corticosteroids), or as labeled, or for whom topical treatments are otherwise medically inadvisable

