#### 8.5 **Prior and Concomitant Therapy**

Any concomitant medication, supplement, or procedure within 6 months before Baseline or received during the study must be recorded, along with:

- Reason for use
- Dates of administration, including start and end dates
- Dosage information, including dose and frequency

Patients may take any medication that is not restricted by the protocol and would not be expected to interfere with the conduct of the study or affect assessments. Chronic medication should be dosed on a stable regimen.

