To ensure that the primary analyses evaluate the effect of study treatment (and not the effect of study treatment + disallowed medications (e.g. topical medications) the following approach will be taken: Patients efficacy data collected after date of first disallowed medication (which may influence efficacy assessments e.g. any medication given to control unacceptable atopic dermatitis symptoms) will be first 'set to missing' / 'treated as missing'. If disallowed medication is introduced the same day as an efficacy assessment, the efficacy assessment will be used as is. Thereafter, the below described analyses should applied.

Primary and secondary efficacy endpoints are to be assessed in the ITT Population. Missing data and data 'treated as missing' for the primary analysis of primary and secondary binary endpoints will be handled with the following multiple imputation method: Intermittent missing data will first be imputed using the MCMC method implemented with the SAS MI procedure, which is appropriate for non-monotonic missing data. Data missing (including 'treated as missing') will then be multiply imputed with the SAS MI procedure using a regression statement (number of imputations: 50, seed: 3628479. At each time point, missing data will be assumed to be MAR and to follow a distribution similar to scores for patients who are still in the study and randomized to the same treatment group.

For categorical efficacy endpoints based on a continuous variable, the multiple imputation will be first done for the continuous variable, then determine the category using the imputed values. Efficacy analyses will be repeated on the PP Population for primary and key secondary endpoints.

When appropriate, the raw parameter, its change from Baseline, and percentage change from Baseline will be summarized.

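### SAP 7.3 counts an adverse event with an unknown start as treatment-emergent even if it resolved before first dose, and leaves open whether the same date rule reaches the disallowed-medication cut-off

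*SAP*

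**What the plan says.** Under its Safety sub-heading, SAP 7.3 has a bullet titled "Missing or incomplete dates in safety data". Listings keep dates as recorded, but "for calculation / sorting / assignation based on dates, the following methods will be used". Item I then deals with an adverse event or concomitant medication whose start is not fully known. It reads: "it is assumed to have occurred during the treatment period (i.e. a TEAE for AEs) except if the partial onset date indicates differently". No day is named for the imputed start, and the stop date is not mentioned.

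Three other places bear on this.

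- **SAP 12.1** (and Protocol 11.8.1) classes adverse events before dosing as pretreatment. Treatment-emergent events are those that begin or worsen after the first dose, up to 7 days after the last.
- **SAP 8.6** defines a prior medication as one taken before the first dose and a concomitant medication as one taken on or after it.
- **SAP 7.3**, in its Efficacy part, sets to missing "patients efficacy data collected after date of first disallowed medication", and Section 9 repeats this. Neither place has a rule for an incomplete medication date, and neither refers to item I.

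Stop dates are available. Protocol 8.5 states "Any concomitant medication, supplement, or procedure within 6 months before Baseline or received during the study must be recorded, along with" the reason, the dose, and the start and end dates. Protocol 11.8.1 has resolution dates of adverse events entered on the eCRF.

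**The concern.** When the start is unknown, a stop date before first dose settles the matter: the event or drug use cannot have begun on treatment. Item I does not use that information. Its one exception depends on the start date, which is the item that is missing.

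For adverse events, this gives a wrong result inside the rule's own scope. Events are collected from informed consent, and screening may precede Baseline by up to 28 days, so the data will contain events that came and went before dosing. Any of them without a usable start date would enter the treatment-emergent tables, including the exposure-adjusted rates.

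For medications, the issue is an unstated link. The primary analysis needs a date of first disallowed medication, and item I is the only place where the SAP handles an incomplete medication start. A programmer could take the derived date from there. Washed-out topicals will be in the medication data, because the protocol looks back 6 months and enrolment usually rests on "Patients having a documented history of inadequate response to treatment with topical medications given for at least 4 weeks" (the alternative is that topicals are medically inadvisable).

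**Working it through.** The plan gives no figure on this point, so the check runs test records through the rules. Dates are counted in days relative to first dose (first dose = 0, which is study Day 1).

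**1. Adverse event, start missing, resolved 20 days before first dose** (an assumed record, within the 28-day screening window).

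- Item I: the start falls in the treatment period, so the event is treatment-emergent.
- SAP 12.1: it was over before dosing, so it is a pretreatment event.
- Consistency check with the SAP 12.1 duration formula (resolution − onset + 1). With the earliest possible imputed start, Day 1: −20 − 0 + 1 = −19 days. With Day 112: −20 − 111 + 1 = −130 days. Every start that item I permits gives a negative duration.

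**2. Adverse event, start known only to the month of first dose, resolved earlier in that month.**

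- The partial start fits both sides of first dose, so the exception does not apply and the event is treatment-emergent.
- A partial start in an earlier month is already protected. The exposed records are those with a fully missing start or an ambiguous partial one.

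**3. Topical medication, start missing, stopped 20 days before first dose.**

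- Protocol Table 3 asks for at least 2 weeks (14 days) off topicals before Baseline; 20 ≥ 14, so the patient complied.
- SAP 8.6 applied first: not taken on or after first dose, hence prior medication. Item I, which speaks of concomitant medication, does not reach it.
- Item I applied first: the start is placed on treatment and the drug becomes concomitant, with a start later than its own stop.
- The SAP does not state the order, though the SAP 8.6 definition favours the first reading.

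**4. What would follow if the item I date were also used as the efficacy cut-off.** The SAP does not say that it is.

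| Derived start | EASI visits set to missing |
|---|---|
| Day 1 | Weeks 2, 4, 8, 12, 16 and 20 (all six) |
| Day 112 | Weeks 16 and 20 at nominal timing |
| Stop date checked first | none |

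In the second row, nominal Week 16 is 16 × 7 = 112 days after first dose, which is study day 113. A Week 16 visit made on or before Day 112, within the ±3-day window, would be kept.

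**5. Size.** The documents give no rate of missing start dates for adverse events or medications. Neither the number of misclassified events nor the number of patients in row 1 or 2 of the table can be derived.

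**The case against.** **A stronger reading that a reader might infer.** One could conclude that the SAP turns washed-out topicals into on-treatment disallowed medication and deletes primary EASI data, at a cost in power. The documents do not support that.

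- Item I is labelled as a rule for safety data, and neither statement of the efficacy trigger refers to it.
- Under SAP 8.6, a topical with a known stop before first dose is a prior medication.
- The trigger is described in on-study terms. Its example is medication given to control unacceptable symptoms, SAP 9.2 speaks of first initiation, and SAP 8.6 tabulates such use over the initial 16 weeks.
- Previous treatments for atopic dermatitis have their own table and listing, separate from concomitant disallowed medication.
- Nothing shows that topical records are especially likely to lack a start date.

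A power loss can only be illustrated. Take the plan's difference of 25 and SD of 43, with a noncentral t calculation. The plan's 47 per arm gives 79.6%, against the stated 80%. From 210/4 × 0.9 = 47.25 evaluable per arm (79.9%), an assumed 2%, 5% or 10% of patients wholly lost leaves 46.3, 44.9 or 42.5 per arm and 79.0%, 77.8% or 75.5% power. The shares are invented, and the loss arises only if the rule is misapplied.

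**The case against raising the point at all.** SAP 12.1 already says that events before dosing are pretreatment, few records will be affected, and supportive analyses on all observed data would show a large misclassification of efficacy data. The small number is plausible, and those analyses are a real check for efficacy. They do not cover adverse events. SAP 12.1 does not cure item I either: the two give different answers for the same record, and item I is the one written for incomplete dates.

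**Conclusion.** The adverse-event rule is wrong as written. It makes some events treatment-emergent that were demonstrably over before dosing, and it conflicts with SAP 12.1. This follows from the text and needs no assumption beyond the existence of such a record.

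Severity is minor. The frequency is unknown. Events that ended before first dose cannot depend on the assigned drug, so they should add to all arms alike: they inflate event counts and blur the comparison rather than favour one arm.

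For medications, the finding is an ambiguity. SAP 8.6 points to the right classification, but item I does not say so, and the SAP does not say whether item I feeds the date of first disallowed medication. If it were reused there, a correctly washed-out patient could lose valid Week 16 EASI values to imputation. The plan does not prescribe that outcome, and no power loss can be derived from the documents.

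**What to change.** 1. **SAP 7.3, item I:** apply the on-treatment assumption only when the stop date is missing or falls on or after the first dose. Otherwise classify the record as a prior medication or a pretreatment event. An incomplete stop date that cannot be placed before first dose counts as missing.
2. **SAP 9 (and the Efficacy part of 7.3):** state that the trigger is first use of a disallowed medication on or after the first dose.
3. **SAP 6.5:** add unresolved start dates of such medications to the agenda of the blinded data review, which is now described only for per-protocol membership. The dates that decide which EASI values count are then fixed before unblinding.

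The cost is a few SAP sentences, a small change to the date-derivation code and one more listing for the review. No change to the protocol or to data collection is needed.
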